5.3.3 Dosage and Administration of Study Medication

Afamelanotide [REDACTED] will be administered [REDACTED] on the designated study days. [REDACTED]

[REDACTED]. Please refer to the CUV801 SOM for further details.

[REDACTED]
[REDACTED]
always within 24 hours of onset of symptoms or last seen well.

5.3.4 Packaging and Labeling of Study Medication

The implant formulation will be packaged in amber glass vials. The label will include information in compliance with the local regulatory requirements for clinical trials/investigational medicinal products.

5.3.5 Storage and Accountability

Study medication will be maintained in a safe and secure (locked, restricted access) location and kept at 2-8°C. The expiry or retest date for each afamelanotide vial will be printed on the label. The Investigator will agree not to supply study drug to any persons other than those enrolled in the study. Current and accurate drug receipts, inventory, accountability and dispensing records will be kept for all study drug in the Pharmacy/Investigator Site File(s), and upon study completion, a final inventory and reconciliation of all study drug will be compiled. [REDACTED]

[REDACTED]
[REDACTED]
[REDACTED]
[REDACTED]

5.3.6 Compliance

Data related to the administration of the study drug will be recorded on the CRF.

5.4 Prior and Concomitant Therapy

5.4.1 Prior Therapy

All subjects (or medical treatment decision makers) will be instructed to report to the Investigator any treatments, prescribed medicines, over-the-counter medications, dietary supplements or nutraceuticals that are being used. Use of any other prior and concomitant therapy which may interfere with the objective of the study, [REDACTED]

5.4.2 Concomitant Therapy

The Investigator must be informed as soon as possible about any medication taken from the time of screening (Day 0, Day of Admission) until the end of the study (Day 42) and these will be fully documented in the patients' medical records and CRF. In the event that a subject has taken a medication which has not been pre-approved, the Investigator will make a decision to continue or discontinue the subject, based on whether the medication may interfere with the objectives of the study.

For complete information, during the study, contraceptive therapy must not be changed.

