5.2.1 Inclusion Criteria

The patients have to fulfill all of the following *inclusion criteria* for study participation:

5.2.4 *Withdrawals and Replacement of Patients*

A discontinuation occurs when a patient does not complete the study as required by the study protocol. Patients will be free to discontinue their participation in this trial at any time for any reason. In addition, patients may be withdrawn from the trial at the discretion of the Investigator or medically qualified nominee. A patient may be withdrawn for any of, but not limited to, the following reasons:

- Informed consent withdrawn by the patient or medical treatment decision maker;
- AE requiring study discontinuation;
- When the Investigator's or nominee's best professional judgment would indicate that it would be in the patient's best interest to be withdrawn;
- Violation of inclusion/exclusion requirements.

The reasons for withdrawal or discontinuation of a patient will be recorded in the patient's medical notes and CRF. If an AE is the reason for discontinuation, the event must be followed up and documented as described in the 5.5.3.2 Safety variables of the protocol. If the patient discontinued for any reason after the enrolment into the study, a study Premature Termination visit, as described in 5.5.1, should be performed at the time of study discontinuation, or as soon as possible after discontinuation. This visit will be documented in the patient's medical notes and CRF.

Any patient(s) withdrawn from the trial prior to their completion for any reason will not be replaced. Data compiled to the point of discontinuation will be used for 'intent to treat' (ITT) analysis. Patients violating any of the inclusion and exclusion criteria will be described as protocol deviators.

5.3 **Study Medication**

5.3.1 *Description of Study Medication*

[REDACTED] afamelanotide
[REDACTED]
[REDACTED]

5.3.2 *Treatment Groups*

There is one treatment group in this study (Open-label study). As such, all patients who satisfy the inclusion/exclusion criteria will be allocated a study subject number and receive afamelanotide. Study subject number allocation will be detailed in the CUV801 Study Operating Manual (SOM).

The groups consist of:

- **Six (6) stroke patients with acute distal (M2 and beyond) LVO or perforator occlusion.**

Open label study: Six (6) patients receiving afamelanotide.

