5.7.2 Efficacy Assessment

5.7.2.1 Specification of Efficacy Endpoints

Primary Endpoints

- (i) *Evaluate the safety of afamelanotide* by monitoring and recording TEAEs (on all days of administration and up to day 42).
TEAEs will be recorded and coded as MedDRA Preferred Terms.

Secondary Endpoints

- (i) *Evaluate changes in the reperfusion of the ischaemic core and the penumbral ischaemic zone* (salvageable tissue) by quantitative analysis of hemodynamics:

[REDACTED]

- [REDACTED]
- [REDACTED]
- [REDACTED]

Upon completion of the study, each patient will generate efficacy after comparing the DWI-FLAIR on Days 3(\pm 1) and 9(\pm 1) with the CTP on Day 0 (Day of Admission).

[REDACTED]

[REDACTED]

[REDACTED]

[REDACTED]

[REDACTED]

5.7.3 *Safety Assessment*

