5.7.3.1 Specification of Safety Endpoint (Primary Endpoint)

The safety endpoint will be the incidence of TEAEs occurring during the study period, including clinically significant changes in laboratory parameters, will be listed by intensity, seriousness, outcome, and relationship to study drug.

5.7.4 *Sample Size*

While this is a phase IIa study of common indication, the sample size is based on availability of patients. A total of six (6) patients are planned to be enrolled in this study. This constitutes an open-label exploratory study.

5.7.5 *Analysis Plan*

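### Section 5.4.2 allows study exit for a medication not approved in advance, and no legible text continues observation to Day 42 after that exit

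*Combined protocol and SAP*

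**What the plan says.** Section 5.4.2 requires the investigator to be told of "any medication taken from the time of screening (Day 0, Day of Admission) until the end of the study (Day 42"). If the medication was not approved in advance, "the Investigator will make a decision to continue or discontinue the subject, based on whether the medication may interfere with the objectives of the study". The legible text gives no list or threshold for that judgement. The related sentence in 5.4.1 is cut off by redaction.

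Section 5.2.4 supplies the meaning of the term: "A discontinuation occurs when a patient does not complete the study as required by the study protocol". It asks for a Premature Termination visit at or soon after discontinuation, and says that data gathered up to that point enter the ITT analysis. It adds: "Any patient(s) withdrawn from the trial prior to their completion for any reason will not be replaced".

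The primary endpoint in 5.7.2.1 is safety, evaluated "by monitoring and recording TEAEs (on all days of administration and up to day 42"). Under 5.1, NIHSS and mRS are done on their scheduled days, ending with Day 42, or at the Premature Termination visit. The Safety Population (5.7.5.1) is everyone enrolled. The ITT population (5.7.5.2) is every treated patient with at least one efficacy assessment after dosing.

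On size and design, 5.7.4 says: "A total of six (6) patients are planned to be enrolled in this study", "the sample size is based on availability of patients", and "This constitutes an open-label exploratory study".

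**The concern.** Taking a further drug after dosing is a post-baseline event. Section 5.4.2 lets that event, together with a judgement by an investigator who knows the treatment and the patient's course so far, end the patient's time in the study. The primary question is which TEAEs occur up to Day 42, and another drug does not stop a TEAE from being recorded. If it clouds causality, 5.5.3.2.5 already has a category for events whose relationship cannot be assessed. If it clouds efficacy, the plan already has a per-protocol population (definition redacted).

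With six patients and no control arm, each exit matters. The patient still counts in the safety denominator but is watched for less time, and has no Day 42 NIHSS or mRS. The exit would also be hard to see in the planned tables: the early-termination summaries in 5.5.3.2 and 5.7.5.8 cover only stops for AEs related to study medication.

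**Working it through.** **1. Is it study exit?** Section 5.4.2 speaks of discontinuing the subject and does not separate study drug from study participation. Section 5.2.4 defines discontinuation by failure to complete the study and follows it with a termination visit. Read together, the legible text means study exit. The visit details in 5.5.1 are redacted, and nothing legible continues observation after that visit.

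**2. What is kept and what is lost.**

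| Item | After exit under 5.4.2 |
|---|---|
| Place in Safety Population | Kept (5.7.5.1) |
| Place in ITT population | Kept, given one post-dose efficacy assessment (5.7.5.2) |
| TEAEs before exit | Counted |
| AEs already known at exit | Followed up under GCP (5.5.3.2.5) |
| NIHSS and mRS at exit | Done at the termination visit (5.1) |
| New TEAEs after exit | Not observed on the legible text |
| NIHSS and mRS at Day 42 | Not observed |

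**3. Follow-up lost.** Inputs: 6 patients (5.7.4) and 42 days (synopsis). Planned follow-up is 6 × 42 = 252 patient-days. One exit on Day d loses (42 − d)/252:

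- Day 4: 38/252 = 15.1%
- Day 8: 34/252 = 13.5%
- Day 16: 26/252 = 10.3%
- Day 21: 21/252 = 8.3%

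Two exits on Day 8 lose 68/252 = 27.0%. These figures measure lost observation; the legible text plans no exposure-adjusted rate.

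**4. Outcomes lost.** One exit removes 1/6 = 16.7% of the Day 42 NIHSS and mRS values.

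**5. Effect on a TEAE count.** Suppose one patient would have had a given event after exit. Because the denominator stays at six, the record changes from 1/6 = 16.7% (exact 95% CI 0.4% to 64.1%) to 0/6 = 0% (0% to 45.9%). Put differently, with no events in n patients watched to Day 42, the one-sided 95% upper bound is 1 − 0.05^(1/n): 39.3% for n = 6, 45.1% for n = 5 and 52.7% for n = 4.

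**6. Effect on an exploratory test (conditional).** The synopsis sets 0.05 two-sided and 5.7 says non-parametric; no test is named legibly. If it were an exact sign or signed-rank test on observed Day 42 changes, the smallest possible p is 2 × (1/2)^n: 0.031 for n = 6 and 0.0625 for n = 5. One missing value would then put 0.05 out of reach. This fails if the termination-visit value stands in for Day 42, which the redacted missing-data section (5.7.5.3) may provide.

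**7. How often?** The documents give no rate. For an assumed risk q per patient, the chance of at least one exit in six is 1 − (1 − q)^6: 26% for q = 5%, 47% for 10%, 74% for 20% and 88% for 30%. This range is illustrative only.

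**The case against.** The strongest reply is that the plan keeps these patients in its analysis sets. A reader might infer that they disappear from the results, or that the efficacy question becomes one about patients who needed no extra medication. The documents do not support either reading. Both population definitions retain the patient, data up to exit are used, and no completers-only analysis is specified. The rule is also narrow: it covers only a drug not approved in advance, it turns on a judgement of interference, and it allows the patient to continue.

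A reader might also infer that TEAE incidence is certainly biased downward and Day 42 scores certainly biased towards a better outcome. That is not supported. If a complication prompts the drug, the complication is itself recorded before exit and the patient already counts as having a TEAE. Only later, different events could be missed. The documents do not say why new drugs would be started.

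It is fair, too, that another drug can confound relationship to study drug and the secondary endpoints, that reasons for withdrawal and all medications go into the CRF, and that in a six-patient descriptive study each exit can be traced. Finally, 5.2.4 allows withdrawal at the investigator's discretion on an open-ended list of grounds, so changing 5.4.2 alone would leave the same route open.

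All of this limits the point. It does not remove the gap: a termination-visit score is not a Day 42 observation, following up known AEs does not detect new ones, and no missing-data rule recovers TEAEs that nobody recorded.

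**Conclusion.** The point holds as a loss of observation after exit. It does not hold as removal from the analysis sets or as a demonstrated bias. Per exit, the cost is one sixth of the Day 42 outcomes and, at Day 8, 13.5% of planned patient-days. One unobserved later event would be enough to turn 1/6 into 0/6. The loss may be informative because the decision follows dosing and is made by someone who knows the patient's course, but its direction and frequency cannot be taken from the documents.

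The conclusion rests on reading 5.4.2 through the definition in 5.2.4, and on the redacted visit details not already providing follow-up to Day 42. If they do, the remaining task is to say so in 5.4.2 and 5.2.4. The p-value figures are secondary, since they rest on an assumed test and on no substitution for missing values. The change is worth making because it is cheap, not because the rule invalidates the study.

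**What to change.** The change concerns data collection only.

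- In 5.4.2, state that use of a medication not approved in advance is recorded (drug, dates, indication), is reported as a protocol deviation where applicable, and does not by itself end follow-up. Planned AE, NIHSS, mRS and imaging assessments continue to Day 42 unless consent is withdrawn.
- Put a matching line in 5.2.4, so that its general discretion to withdraw does not reopen the same gap.
- Keep these patients in the safety and main efficacy summaries, flag them in the listings, and add a sensitivity listing without them.

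Which medications are acceptable, and whether study drug continues, are clinical matters that this point leaves alone.

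The cost is two short pieces of protocol wording, a flag and one extra listing. No visits, procedures or patients are added to those already planned. The small downside is that the efficacy summaries will include patients whose recovery may be affected by another drug; the flag and the sensitivity listing make that visible.

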5.5 Study Procedures

This will be an inpatient study (during hospital admission). [REDACTED]

[REDACTED] Patients may be discharged and will be asked to return to hospital for the rest of study visits. Patients will participate for a total of up to nine visits.

[REDACTED]

[REDACTED]

[REDACTED]

[REDACTED]

[REDACTED]

[REDACTED]

[REDACTED]

[REDACTED]

[REDACTED]

[REDACTED]

[REDACTED]

[REDACTED]

[REDACTED]

[REDACTED]

[REDACTED]

[REDACTED]

[REDACTED]

[REDACTED]

[REDACTED]

[REDACTED]

[REDACTED]

[REDACTED]

[REDACTED]

[REDACTED]

[REDACTED]

[REDACTED]

[REDACTED]

[REDACTED]

[REDACTED]

- | [REDACTED]
- | [REDACTED]
- | [REDACTED]
- | [REDACTED]
- | [REDACTED]

[REDACTED]

[REDACTED]

- | [REDACTED]
- | [REDACTED]
- | [REDACTED]
- | [REDACTED]
- | [REDACTED]
- | [REDACTED]

[REDACTED]

- | [REDACTED]
- | [REDACTED]
- | [REDACTED]

[REDACTED]

[REDACTED]

- | [REDACTED]
- | [REDACTED]
- | [REDACTED]
- | [REDACTED]

[REDACTED]

[REDACTED]

[REDACTED]

[REDACTED]

[REDACTED]

[REDACTED]

[REDACTED]

[REDACTED]

[REDACTED]

[REDACTED]

[REDACTED]

[REDACTED]

[REDACTED]

[REDACTED]

[REDACTED]

[REDACTED]

[REDACTED]

[REDACTED]

[REDACTED]

[REDACTED]

[REDACTED]

[REDACTED]

[REDACTED]

[REDACTED]

[REDACTED]

[REDACTED]

[REDACTED]

[REDACTED]

[REDACTED]

5.5.2 *Study Procedures Flowchart*

Please refer to the section [Study Flow Chart](#) of the protocol.

5.5.3 *Methods of Assessment*

5.5.3.1 Efficacy Variables

The Efficacy of the treatment will be assessed by:

5.5.3.1.1 Evaluation of MRI imaging (CTP and DWI-FLAIR)

Background

For patients with acute arterial occlusion,

[REDACTED]

[REDACTED]

MRI diffusion weighted imaging (DWI) is accurate in the identification of acutely infarcted tissue.

[REDACTED]

Imaging Protocol

Standard care multimodal computed tomography (CT) will be performed on Day 0. [REDACTED]

[REDACTED]

MRI will be performed at Days 3(\pm 1) and 9(\pm 1) [REDACTED]

[REDACTED]

Efficacy of treatment

[REDACTED]

[REDACTED]

[REDACTED]

5.5.3.1.2 Modified Rankin Scale (mRS)

The mRS (see Appendix A) indicates the degree of disability or dependence in the daily activities of patients who have suffered a stroke or other causes of neurological disability.

The mRS will be performed on Days 0, 7 and 42.

5.5.3.1.3 National Institutional Health Stroke Scale (NIHSS)

The validated NIHSS (see Appendix B) records the level of impairment caused by a stroke in 11 items.

A score assessed in 582 patients illustrated the distribution of mild, moderate and severe AIS.

A score equal or less than 8	mild AIS	[19.8%]
A score between 9 and 15	moderate AIS	[30.3%]
A score equal or above 16	severe AIS	[49.9%]

Table 2. NIHSS scores

Score ^[3]	Stroke severity
0	No stroke symptoms
1–4	Minor stroke
5–15	Moderate stroke
16–20	Moderate to severe stroke

21-42	Severe stroke
-------	---------------

[REDACTED]

5.5.3.2 Safety Variables

The number of patients with treatment-emergent AEs (TEAEs) will be summarized by MedDRA preferred term and body system. TEAEs will be further summarized by intensity, seriousness, outcome and relationship to study drug. Patients who prematurely terminate treatment due to AEs related to study medication will be summarized.

5.5.3.2.1 Clinical Laboratory Evaluations

[REDACTED]

[REDACTED]

[REDACTED]

[REDACTED]

[REDACTED]	[REDACTED]	[REDACTED]
[REDACTED]	[REDACTED]	[REDACTED]
[REDACTED]	[REDACTED]	[REDACTED]
[REDACTED]	[REDACTED]	[REDACTED]
[REDACTED]	[REDACTED]	[REDACTED]
[REDACTED]	[REDACTED]	[REDACTED]

[REDACTED]

[REDACTED]

The Investigator will sign and date all laboratory reports and review all laboratory test results as soon as possible. The Investigator will evaluate the clinical significance of all values outside the reference range and will document within the laboratory report as well as in the patient's CRF. If a laboratory value is outside the reference range and felt to represent a clinically significant change from the baseline value, this will be reported as an AE in the patient's medical notes and on the AE CRF page. An assessment of this AE will be made by the Investigator, in particular regarding the relationship of the event to the study drug.

5.5.3.2.2 General Physical Examination

A general physical examination will be performed [REDACTED]

Weight and Height

Weight in kilograms will be recorded [REDACTED]
[REDACTED]
[REDACTED]

5.5.3.2.3 Neurological examination

Neurological examination using a NIHSS will be conducted in a standardized manner [REDACTED]
[REDACTED]
[REDACTED]

5.5.3.2.4 Vital Signs Measurements

Vital signs (blood pressure, temperature and pulse rate) will be recorded [REDACTED]
[REDACTED]
[REDACTED]

5.5.3.2.5 Adverse Events

An adverse event (AE) is defined as any untoward medical event (clinical or laboratory) experienced by a patient during the course of a clinical trial, whether or not it is related to the investigational product. An AE may be a symptom, sign, or abnormal finding or test result. Whenever possible, the Investigator will group together into a single term, signs and symptoms that constitute a single diagnosis. For example, cough, rhinitis and sneezing might be grouped together as "upper respiratory tract infection".

The Investigator will monitor each patient closely for the development of AEs, and any adverse experience spontaneously reported by or elicited from the patient or observed by the Investigators (physician or study staff) will be recorded in the patient's medical notes and on the appropriate AE page of the CRF, when applicable. [REDACTED]

[REDACTED]
[REDACTED]
[REDACTED]

[REDACTED] It is the responsibility of any member of the study site staff to immediately report any suspected AE to the Investigator.

The Investigator will assess the AE(s) in the patient's medical notes and provide the date and time of onset, severity, seriousness, action taken, outcome, date of resolution (or comment that the event is still continuing) and relationship to study medication.

If a laboratory value is outside the normal range, the Investigator must comment on the findings in the laboratory report. For any clinical laboratory abnormality, the Investigator will make a judgment as to clinical significance. All clinically significant laboratory abnormalities will be recorded as an AE in the patient's medical notes and on the AE page of the CRF.

All AEs will be followed up in accordance with GCP. AEs will be graded for severity as defined below:

- **Mild** - The AE is transient and easily tolerated by the patient. Specific action is optional;
- **Moderate** - The AE causes the patient discomfort and interrupts the patient's usual activities;
- **Severe** - The AE causes considerable interference with the patient's usual activities and may be incapacitating or life-threatening.

Outcome of the event must be described as one of the following:

- Recovered without sequelae;
- Recovered with sequelae;
- Recovering;
- Not recovered;
- Death.

The Investigator will be asked to document his/her opinion of the relationship of the event to the study drug as follows:

- **Related** - There are facts or arguments to suggest a causal relationship, i.e. there is a reasonable possibility of a causal relationship between the drug and the AE(s);
- **Not Related** - There is not a reasonable possibility that the AE(s) is/are related to the drug – alternative aetiology, diagnosis, or explanations for the AE(s) exist, or the time from suspect drug intake make a relationship improbable;
- **Not Assessable** - Report suggesting an adverse reaction BUT cannot be judged because information is insufficient or contradictory OR cannot be supplemented or verified.

Serious Adverse Events (SAE)

A Serious Adverse Event (SAE) is any adverse event occurring at any dose that results in any of the following outcomes:

- Death (due to any cause);
- Is life-threatening;
- Requires a prolongation of an existing hospitalization.
- Results in a persistent or significant disability/incapacity;
- Is a congenital anomaly/birth defect;
- Important medical events that may not be immediately life threatening, result in death or require prolonged hospitalization but may be considered a SAE when, based upon appropriate medical judgment, they may jeopardize the patient or may require medical or surgical intervention to prevent one of the outcomes listed in the definition above.

Reporting: Any SAE, including death due to any cause, which occurs during this study, has to be reported to CLINUVEL **within 24 hours** of the Investigator or their delegate becoming aware of the event, even if only limited information regarding the event is available. The CLINUVEL safety team will follow up on any missing information or any other information needed and it is expected that the investigator responds to these queries as the information becomes available.

An SAE report form must be completed and sent to CLINUVEL Safety Team at [REDACTED] or sent by fax to the number provided in the form within 24 hours of the event occurring or within 24 hours of becoming aware of the event. In addition to completing the SAE report form (one form completed for each SAE), additional supporting information should be provided as appropriate, such as photocopies of pertinent test results and medical notes, trial records, consultant report(s), hospital discharge summary and autopsy report (if relevant and as soon as available to the Investigator). All SAEs will be recorded in the patient's medical notes and on the AE page of the CRF.

The Investigator will determine whether the seriousness of the event warrants removal of any patient from the study. The Investigator will institute appropriate diagnostic and therapeutic measures and keep the patient under observation for as long as is medically indicated.

Certain AEs and/or SAEs, including suspected unexpected serious adverse reactions (SUSARs), may warrant expediting to HRECs, according to the regulatory requirements for the individual countries or sites involved, either by the Investigator or the Sponsor. The modalities for reporting and filing relevant documentation will be detailed in the CUV801 SOM.

[REDACTED]

[REDACTED]

Pregnancy and/or Breastfeeding

The following situations must be reported to CLINUVEL **within 24 hours** of the Investigator or their delegate becoming aware of the event, even if only limited information regarding the event is available.

- Pregnancy occurring in a female patient, when dose was administered less than three months after the last afamelanotide;
- Pregnancy occurring in the female partner of a male patient treated, when the start of the pregnancy is less than three months after the last afamelanotide dose was administered to the male patient;
- Female patient breastfeeding when less than three months after the last afamelanotide dose was administered;
- Birth of a child from a female patient, when the start of the pregnancy was less than three months after the last afamelanotide dose was administered;
- Birth of a child from the female partner of a male patient, when the start of the pregnancy is less than three months after the last afamelanotide dose was administered to the male patient.

[REDACTED] Report Form and/or a Pregnancy Outcome/Breastfeeding Report form will be completed and sent to the CLINUVEL Safety Team at [REDACTED] or faxed to the number provided in the forms within 24 hours of becoming aware of the event. All pregnancies will be followed from the date of pregnancy detection until pregnancy outcome and/or lactation (when applicable).

Female patients who become pregnant, give birth or begin breastfeeding during the treatment period will be withdrawn from treatment and complete the Premature Termination Visit.

For male patients of female partners who become pregnant, the responsible Investigator will determine whether the event warrants removal of any patient from the study.

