5.0 INVESTIGATIONAL PLAN

5.1 Overall Design and Plan of the Study

This is an open label phase IIa pilot study to be conducted in six (6) patients with acute AIS during a 6-weeks period [REDACTED]

To determine eligibility for entry into the study, [REDACTED]
[REDACTED] Eligible patients will be enrolled and will be administered [REDACTED]
[REDACTED]

[REDACTED]

[REDACTED]

The results will be reviewed on the basis of a benefit: risk assessment. If the benefit: risk assessment is in favour of afamelanotide, in the opinion of the Investigator, [REDACTED]

Radiological evaluation by assessing the imaging from Computed Tomography Perfusion (CTP)

Clinical evaluations will be performed by accredited study staff over the course of the study. The NIHSS will be performed at the Day of Admission (Day 0) and on Days 1, 2, 3, 4, 7, 8 and 42 or Premature Termination Visit (if applicable). The modified Rankin Scale (mRS) will be performed on Days 0, 7 and 42 or Premature Termination Visit (if applicable). [REDACTED]

Safety assessments (review of AEs and concomitant medications) will be carried out each day (each study visit from the Day of Admission to Day 8 and Day 42 or Premature Termination Visit).

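### The SAE definition counts only a prolonged hospital stay, so a readmission after discharge is not serious on that ground and can miss 24-hour reporting and the seriousness tables

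*Combined protocol and SAP*

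**What the plan says.** Section 5.5.3.2.5 lists six outcomes that make an adverse event serious: death, threat to life, a hospitalization criterion, persistent or significant disability, congenital anomaly, and important medical events. The hospitalization criterion reads "Requires a prolongation of an existing hospitalization". The important-medical-event item uses the same narrow idea, referring to events that may not "result in death or require prolonged hospitalization but may be considered a SAE when, based upon appropriate medical judgment", they meet one of two conditions: "they may jeopardize the patient or may require medical or surgical intervention to prevent one of the outcomes listed in the definition above". The list shows no redaction.

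Section 5.5 describes an inpatient study but adds: "Patients may be discharged and will be asked to return to hospital for the rest of study visits". Section 5.1 places safety review at "each study visit from the Day of Admission to Day 8 and Day 42 or Premature Termination Visit".

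Two things depend on the serious classification:

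- **Reporting.** Section 5.5.3.2.5 states: "Any SAE, including death due to any cause, which occurs during this study, has to be reported to CLINUVEL", with a 24-hour limit.
- **Analysis.** Section 5.5.3.2 states: "TEAEs will be further summarized by intensity, seriousness, outcome and relationship to study drug". Section 5.7.3.1 includes seriousness in the specification of the primary endpoint, and section 5.7.5.8 adds an individual listing of SAEs.

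**The concern.** The definition fits a patient who never leaves hospital. The protocol allows discharge and then follows patients to Day 42, so the definition does not fit the whole period over which events are collected. For a stroke patient at home, an unplanned admission (for recurrent stroke, infection or a fall, say) is among the main serious outcomes to be expected. As written, that admission does not make the event serious.

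Safety is the only primary objective, the trial has no comparator, and the use of the drug is new. A readmission recorded as non-serious would understate the SAE count and would not trigger the mandatory 24-hour report. Two investigators could also classify the same event differently, and both would be following the protocol.

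**Working it through.** The plan has no figure of its own to reproduce: section 5.7.4 bases the six patients on availability, and no event rate is stated. The main check is therefore a reading of the text. The arithmetic only gives scale.

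**1. Apply the criteria to a discharged patient.** Take an infection after discharge that needs admission but is neither life-threatening nor disabling.

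- Death, threat to life, disability, congenital anomaly: not met.
- Hospitalization criterion: not met, because there was no stay to prolong when the event began.
- Important medical event, intervention condition: it covers intervention to prevent a listed outcome. A new admission is not a listed outcome, so averting or needing one does not count.
- Important medical event, jeopardy condition: possible, but left to medical judgment.

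**2. Apply the criteria to an inpatient.** If the same infection lengthens the stay of a patient still in hospital, it is serious without any judgment. The classification thus depends on where the patient was when the event began.

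**3. Time at risk.** Safety review is scheduled to Day 8 and then at Day 42. The interval is 42 − 8 = 34 days, or 34/42 = 81% of follow-up. This is the span after Day 8, not measured outpatient time; the visible text does not say when discharge occurs.

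**4. Chance of any readmission.** The per-patient probability *p* by Day 42 is an assumption. With six independent patients, the expected number is 6*p* and P(at least one) = 1 − (1 − *p*)^6.

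| Assumed *p* | Expected readmitted, of 6 | P(at least one) |
|---|---|---|
| 2% | 0.12 | 11.4% |
| 5% | 0.3 | 26.5% |
| 10% | 0.6 | 46.9% |
| 15% | 0.9 | 62.3% |
| 20% | 1.2 | 73.8% |

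**5. Chance that a readmission escapes.** Suppose further that a fraction *f* of readmissions meets no other criterion and is not judged serious. Then P(at least one escapes) = 1 − (1 − *pf*)^6.

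- *p* = 5%, *f* = 10%: 1 − 0.995^6 = 3%.
- *p* = 15%, *f* = 30%: 1 − 0.955^6 = 24%.

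Both *p* and *f* are assumptions.

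**6. Effect on the summary.** Exact (Clopper-Pearson) 95% intervals, if one readmission is the only candidate SAE:

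- Not counted: 0/6 = 0% (0 to 45.9%); the upper limit is 1 − 0.025^(1/6).
- Counted: 1/6 = 16.7% (0.4 to 64.1%).

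The intervals overlap heavily, but the reported finding changes from no SAE to one.

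**The case against.** The strongest reply is that few readmissions would actually be lost. A recurrent stroke would usually qualify as disabling or life-threatening, and an infection or fall bad enough for admission would often be judged to jeopardize the patient. The 26% to 62% range is the chance of any readmission, not of a misclassified one; step 5 gives a smaller range. This is a fair limit on the likely size.

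The event would also stay visible. Section 5.7.5.8 lists every AE, and the TEAE count itself does not change if the event meets that definition. Section 5.5.3.2.5 requires staff to tell the investigator at once of any suspected AE and allows some AEs, not only SAEs, to be expedited to ethics committees. Section 5.7.5.11 permits safety review between visits. This also stands, but none of these routes replaces the mandatory 24-hour report to the sponsor or the SAE listing.

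Last, parts of sections 5.5 and 5.5.3.2.5 are redacted, and the Study Operating Manual and SAE form are not in the documents. Any of these might address readmission. They could not repair the definition, however: its list is complete and unredacted, and a broader instruction elsewhere would conflict with it.

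**Conclusion.** The concern holds. The gap is in the wording and does not depend on any assumed rate: a new admission is not a ground for seriousness, and the fallback clause is discretionary and repeats the reference to a prolonged stay. An investigator who follows the definition exactly could record a discharged patient's readmission as non-serious.

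How often this would happen cannot be taken from the documents. Under the assumptions shown, the chance of at least one readmission in six patients is 26% to 62%, and the chance of at least one being misclassified is about 3% to 24%. What is lost is the serious classification, the 24-hour report and the individual listing, not the AE record. In a six-patient, single-arm safety study, each such event is worth 16.7 percentage points of the SAE proportion. The definition should be corrected.

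**What to change.** In the section 5.5.3.2.5 hospitalization criterion, insert the words *inpatient hospitalization or* ahead of the reference to prolongation, so that either a new admission or a lengthened stay makes an event serious. Make the matching change in the important-medical-event item. Check that the SAE report form and the Study Operating Manual use the same definition, and amend them if they do not.

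This is a one-phrase protocol amendment, repeated once. It brings the definition into line with the discharge provision in section 5.5 and with follow-up to Day 42. The cost is a few more SAE forms and possibly a higher SAE count; no sample size or analysis method changes.
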